7.4.2 Predictor variables

Motivation to Quit Smoking (Contemplation Ladder): The contemplation ladder will be used to assess readiness to consider smoking cessation [59]. The contemplation ladder is designed to measure a smokers position on an 11-point scale (0-10) range, from having no thought of quitting to taking action to quit, and has been successfully employed in several diverse smoking populations [60-62]. We will assess changes in quitting motivation from Intake to Day 22 (end of study).

Craving: Craving will be measured on Day 6 with the well-validated and reliable 10-item brief Questionnaire of Smoking Urges [48-50]. Items are scored from (1=strongly disagree to 7=strongly agree).

Withdrawal symptoms will be measured on Day 6 with the Minnesota Nicotine Withdrawal Scale [51]. This 15-item scale assess withdrawal symptoms with respect to a specific frame of time (0=none to 4=severe).

Subjective rewarding value of IQOS will be measured on Day 6 with the Cigarette Evaluation Scale (CES) adapted for IQOS use [15-18,27]. The CES is an 11 item Likert-format (1=not at all to 7=extremely) self-report instrument with established validity and reliability ($\alpha > .80$) [22,23,32,33,52]. We will focus on the Satisfaction Subscale for the measurement of subjective reward [23].

IQOS Risk perceptions will be measured on Day 6 with 12 items. Four items drawn from prior studies will assess absolute health risk and addictive potential [53-56]. Response options include 1=no risk, 2=low risk, 3=moderate risk, 4= high risk, and 5=very high risk. Eight previously validated tobacco use risk perception items will assess risk relative to combustible cigarettes [57,58]. Instructions are "Compared to your own cigarettes that you usually smoke, IQOS is lower in nicotine, lower in tar, are less addictive, are less likely to cause cancer, have fewer chemicals, are healthier, make tobacco use safer, and help people quit smoking." The Likert-style response options range from 1=definitely untrue to 5=definitely true [57,58].

CONFIDENTIAL

This material is the property of the University of Pennsylvania. Do not disclose or use except as authorized in writing by the study sponsor

Relative reinforcing value of IQOS will be measured on Day 7 with a validated choice paradigm, evaluating the preference for IQOS versus cigarettes [34,36,37]. RRV will be defined in relation to responding for cigarette puffs. Working for cigarette puffs on \leq 5 trials out of the 10 trials is indicative of reinforcer indifference or less reinforcing value of cigarette puffs relative to IQOS puffs [41,42]. We will also measure overall responding for IQOS versus cigarette puffs [41,42].

IQOS Use will be determined by counting the daily spent tobacco HeatSticks returned for each of the 14 days (days 8 – 21) [12] [24,25]. HeatSticks per day will be included as a time-varying covariate in the Aim 1 models.

7.4.3 Outcome variables

Cigarette Consumption (primary outcome): The primary outcome is the longitudinal daily count of cigarettes from Intake to the end of the IQOS switch phase. Daily cigarette consumption will be determined by counting the daily spent cigarette filters returned for each of the 14 days (days 8-21).

Motivation for smoking cessation (secondary outcome): The contemplation ladder will be used to assess readiness to consider smoking cessation. The contemplation ladder is designed to measure a smoker's position on an 11-point scale (0-10) range, from having no thought of quitting to taking action to quit, and has been successfully employed in several diverse smoking populations [60, 62]. We will assess changes in quitting motivation from baseline to day 21 (end of study).

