4.1 General Design

We propose to conduct a within-subjects study of the impact of IQOS use on smoking behavior among 160 combustible cigarette smokers. Eligible smokers will participate in 8 visits across a 21-day protocol. Participants who are eligible based on telephone screening will complete an in-person Intake Visit (**day 0**). Those eligible will complete measures of demographics, smoking history, and motivation to quit smoking. Baseline cigarette smoking rate will be established during **days 1-5** by instructing participants to smoke as usual for the following five days (**days 1-5**), while collecting their spent cigarette filters each day. Participants will return to the lab on **day 6** after overnight smoking abstinence (CO < 10). Participants will be required to use the IQOS device in the lab, then complete an assessment of IQOS-associated craving relief, withdrawal relief, subjective rewarding value of IQOS, and IQOS-associated risk perceptions. Participants will also return to the Center on **day 7** after overnight smoking abstinence (CO value 50% of Intake visit's CO value) for an assessment of the Relative Reinforcing Value of IQOS (RRVI) after required use of the IQOS device in the lab. **See Figure 1.**

Participants will then be instructed to use IQOS (versus cigarettes) for the following 14 days (**days 8-21**). Participants will collect their used cigarette filters and their used IQOS HeatSticks daily in order to assess consumption of cigarettes per day and sticks per day. Participants will return to the Center on days 11, 14, 17, and 21 to have their carbon monoxide (CO, exhaled breath) measured, and to return their used tobacco sticks and any spent cigarette filters. Cigarette smoking status will be assessed via self-report, spent cigarette filters, and biochemically verified (CO value 50% of Intake visit's CO value). Changes in motivation to quit smoking will be measured at study end, and all remaining used sticks and spent cigarette filters will be returned on Day 22.

On Day 22, participants will be: (1) informed of the lack of data supporting IQOS as a smoking cessation aid or harm reduction tool; (2) cautioned on the likelihood of dual use and the risks

CONFIDENTIAL

This material is the property of the University of Pennsylvania. Do not disclose or use except as authorized in writing by the study sponsor

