7.2.3 Day 6 Visit

During the Day 6 Visit, (Duration: ~1.25 hours) participants will:

1. Arrive at the Center at 9:00 AM after having abstained from smoking overnight.
2. Perform a CO breath assessment and concomitant medication review.
3. Be asked questions about use of marijuana, other tobacco products (besides cigarettes), or vaping of any substance including tobacco/nicotine or other drugs in the past month.
4. Have their overnight smoking abstinence (10-hours) verified by a CO measurement of 50% of Intake visit's CO value
5. Return five date-stamped zipped baggies containing all spent cigarette filters from Days 1-5.
6. Receive instructions on how to use the IQOS prior to two IQOS HeatStick exposures (one regular, one menthol).
7. Be required to use the IQOS device in the lab, where they will be exposed to two IQOS HeatSticks (one regular, one menthol)
 - Participants will take 14 puffs from the regular HeatStick, then take 14 puffs from the menthol HeatStick. These two exposures will be separated by 45 minutes.

[figure not shown]
CONFIDENTIAL

This material is the property of the University of Pennsylvania. Do not disclose or use except as authorized in writing by the study sponsor

8. Complete questionnaires after each exposure:

- Adverse Events Form (Open-Ended AEs)
- Questionnaire of Smoking Withdrawal Symptoms (MNWS)
- IQOS Risk Perceptions
- Subjective Reward of IQOS (CES adapted for IQOS use)

9. Be reminded to engage in overnight smoking abstinence (10-hours) in preparation for the Day 7 Visit.

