7.2.5 Day 11 Visit

During the Day 11 Visit (duration: ~30 min), participants will:

1. Perform a CO breath assessment and concomitant medication review.
2. Be asked questions about use of marijuana, other tobacco products (besides cigarettes), or vaping of any substance including tobacco/nicotine or other drugs in the past month.
3. Complete questionnaires:
 - Adverse Events Form (Open-Ended AEs)
4. Return used HeatSticks (and cigarette filters, if applicable) in date-stamped zipped baggies provided by the research staff.

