7.2.6 Day 14 Visit

During the Day 14 visit (duration: ~30 min) participants will:

1. Perform a CO breath assessment and concomitant medication review.

CONFIDENTIAL

This material is the property of the University of Pennsylvania. Do not disclose or use except as authorized in writing by the study sponsor

2. Be asked questions about use of marijuana, other tobacco products (besides cigarettes), or vaping of any substance including tobacco/nicotine or other drugs in the past month.
3. Complete questionnaires:
 - Adverse Events Form (Open-Ended AEs)
4. Return used HeatSticks (and cigarette filters, if applicable) in date-stamped zipped baggies provided by the research staff.
5. Receive second seven-day supply of HeatSticks, and 14 date-stamped zipped baggies for daily collection of spent filters and HeatSticks (7 for spent cigarette filters, 7 for used HeatSticks).

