7.2.9 Day 22 Visit

During the Day 22 visit (Duration: ~30 min) participants will:

1. Complete questionnaires:
 - Adverse Events Form (Open-Ended AEs)
 - Concomitant medication review
 - Changes in motivation to quit smoking (Contemplation Ladder)
2. Return all remaining used HeatSticks and spent cigarette filters
3. Be informed of the lack of data supporting IQOS as a smoking cessation aid or harm reduction tool
4. Cautioned on the likelihood of dual use and the risks associated with dual use
5. Advised to either quit using IQOS or quit smoking cigarettes if they are using both
6. Referred to a smoking cessation program if interested in quitting smoking

CONFIDENTIAL

This material is the property of the University of Pennsylvania. Do not disclose or use except as authorized in writing by the study sponsor

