assessment will inquire about any event(s) or symptom(s) experienced since the last in-person visit. If a participant reports a symptom or medical event, they will be asked to rate the severity of the event utilizing the following severity scale: 0 (None=No Concerns), 1 (Mild=Issue does not interfere with usual daily activities), 2 (Moderate=Issue does interfere with some activities), and 3 (Severe=No normal activities are possible). See section 8.2.1: AE Collection Methods for further details.

Carbon Monoxide (CO) will be measured using a Vitograph CO monitor (Lenexa, KS). A CO > 5 is indicative of combustible cigarette smoking [25,45,46]. HNB products are expected to result in significantly lower increases in CO compared to a combustible cigarettes [47]. Five minutes of IQOS use did not result in clinically significant increases in CO (0.3 ppm) after overnight abstinence compared to five minutes of combustible cigarette [27]. We will include CO as a covariate in our statistical models.

Concomitant Medications: At the Intake Visit, participants will be asked to list all medications (prescription or non-prescription) and NRTs currently taken and/or recently discontinued (within the past 14 days) as a baseline collection. All information will be collected on a Concomitant Medication Log that will be maintained within the participant's study chart. At every subsequent in-person visit, participants will be asked if they have taken any additional medications (prescription or non-prescription), NRTs, and/or changed the dosage or stopped taking any previously reported medications since their last in-person visit. Participants who report taking contraindicated medication(s) over the course of the study period may only remain eligible if the Principal Investigator determine that the contraindicated medication(s) did not impact the study design, data quality, and/or participant safety and welfare.

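### A switch-phase day with no filter bag may be a smoke-free day or a lost or withheld bag, and the plan has no record or scoring rule that separates the two

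*Combined protocol and SAP*

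**What the plan says.** Section 7.4.3 sets the measurement rule for the primary outcome: "Daily cigarette consumption will be determined by counting the daily spent cigarette filters returned for each of the 14 days (days 8-21". The item lists for the Day 11, 14, 17 and 21 visits (Sections 7.2.5 to 7.2.8) share one return instruction: "Return used HeatSticks (and cigarette filters, if applicable) in date-stamped zipped baggies provided by the research staff". The baseline instruction in Section 7.2.3 has no such condition: "Return five date-stamped zipped baggies containing all spent cigarette filters from Days 1-5". At the final visit (Section 7.2.9) participants "Return all remaining used HeatSticks and spent cigarette filters".

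One filter bag exists for each switch-phase day. Sections 7.2.4 and 7.2.6 each issue fourteen bags for a week ("7 for spent cigarette filters, 7 for used HeatSticks").

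On other sources, Section 4.1 states: "Cigarette smoking status will be assessed via self-report, spent cigarette filters, and biochemically verified". Section 7.4.1 makes CO a model covariate and says "A CO > 5 is indicative of combustible cigarette smoking". Section 7.5 leaves the missing-data method to be chosen once the data are in hand, expects over-dispersed and possibly zero-inflated counts, and tests H1a by the contrast between the baseline and switch phases.

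**The concern.** The condition on filters most naturally means that they come back if any cigarettes were smoked. A participant who smoked nothing on a given day then properly hands in no filters for it. So does a participant who smoked and lost or withheld the bag. No section asks for the empty bag, has staff record bag status, or says how a day without a bag is scored.

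This is more than a detail left for later, because analysis cannot repair it. A missing-data method needs to know which days are missing, and here they look the same as true zeros. Zeros are also expected, so false ones will not stand out.

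Two results are exposed: the H1a phase contrast, and the Aim 1 summary of cigarette-only, dual-use and complete-switching days. In that summary, a false zero on a day with HeatSticks returned turns dual use into complete switching.

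**Working it through.** **1. The plan's own figure.** Section 7.5 gives a detectable slope of 0.1 per day, or 1.5 cigarettes per day across the switch period (r = 0.6), and 0.15 per day, or 2.0 (r = 0.3). Slope times 14 days gives 1.4 and 2.1, consistent after rounding. The figures cannot be reproduced, because no mean, SD or dispersion is given. A linear approximation, slope = (1.96 + 0.84) × SD × √((1 − r)/(227.5 × N)), implies a daily SD of about 8.5 (r = 0.6) or 9.7 (r = 0.3) at N = 100, and 10.8 or 12.2 at N = 160. These are changes along a slope. Constant under-return produces a step at Day 8, so they are not a yardstick for the bias below.

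**2. Bias when an unreturned bag is counted as zero.** Let m_B and m_S be the true mean cigarettes per day at baseline and in the switch phase, and p_B and p_S the shares of smoking-day bags lost. For losses unrelated to the amount smoked:

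observed contrast = (1 − p_S)m_S − (1 − p_B)m_B = (m_S − m_B) − p_S·m_S + p_B·m_B

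- No true change (m_S = m_B = m): bias = −(p_S − p_B) × m. A 5% differential gives 0.05 × 10 = 0.5 and 0.05 × 15 = 0.75. A 10% differential gives 1.0 and 1.5.
- Equal loss p: the contrast becomes (1 − p)(m_S − m_B). The bias is nil with no true change, and a real fall is shrunk slightly.
- One of 14 bags lost by one participant: a false fall of m/14, or 0.71 at 10 per day and 1.07 at 15.

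The rates of 10 and 15 per day and all loss shares are assumptions. The documents give only an entry minimum of 5 per day.

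**3. Both simple codings fail when there is real switching.** Assume 15 per day on smoking days, 30% true IQOS-only days, complete baseline return, and no empty bags handed in.

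- Truth: 0.70 × 15 = 10.5, a fall of 4.5.
- 5% of smoking-day bags lost and counted as zero: 0.70 × 0.95 × 15 = 9.975, an apparent fall of 5.025 (inflated by 0.525).
- Every day without a bag coded missing: mean 15, an apparent fall of 0.

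**4. Effect on the test.** Simulated gamma-Poisson daily counts: 5 baseline and 14 switch days, no true change, mean 10 (SD 6) or 15 (SD 8.5), r = 0.3 or 0.6, N = 100 (the figure in Section 7.5) or 160 (Section 4.1), losses at random. The test was on the mean within-subject difference, a simplification of the planned mixed model.

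| Switch-phase bags lost, counted as zero | False fall per day | Null rejected (nominal 5%) |
|---|---|---|
| 2% | about 0.2 to 0.3 | 10 to 25% |
| 5% | 0.5 to 0.75 | 46 to 90% |
| 10% | 1.0 to 1.5 | 96 to 100% |

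Coding the same lost bags as missing, which requires knowing which they are, gives a bias of about 0 and rejection in 4 to 6% of runs. Equal loss in both phases, counted as zero, gives about 4 to 7%.

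**5. IQOS-only days.** With 30% true IQOS-only days, 5% loss on the rest gives at most 0.30 + 0.70 × 0.05 = 33.5%, and 10% gives at most 37%. These are upper bounds: an affected day with no HeatSticks recorded shows no product at all, not complete switching.

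**6. Could another record separate the two cases?**

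- Self-report: the Day 11 to 21 lists ask about tobacco other than cigarettes. A cigarette self-report (past 24 hours) is listed only at Intake.
- Accountability log (Section 6.3): it compares product dispensed with product returned. Cigarettes are not dispensed (heading 4.1.4), so there is no total to check against.
- CO: four switch-phase readings cannot check 14 daily counts, and no rule covers a zero count with a raised reading.

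**The case against.** The strongest reply is that the plan nowhere scores an absent bag as zero. That is right. A reader might infer it from the counting rule, but Section 7.4.3 is silent and Section 7.5 leaves the missing-data method open. What survives is that neither coding is safe without a record of bag status.

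A reader might also infer that bags are optional in the switch phase. The documents do not support this: filters are to be collected daily, a bag is issued for each day, and Day 22 asks for whatever remains. Even so, a smoke-free day's bag need not come back.

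Nor is the error necessarily one-sided. A lost baseline bag biases the other way, and Section 7.2.3 has no rule for one either. Table 2 pays for returned material in both phases: $35/5 = $7 per baseline day against ($45 + $45 + $45 + $60 + $15)/14 = $15 per switch day, which could make baseline return the poorer. That payment covers cigarettes and HeatSticks together, so it does not secure the filter bags. Worse return after the instruction to switch completely is plausible but assumed.

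It is also tempting to say that a loss of 10% or so manufactures the plan's whole detectable effect. That sets a step against a slope-based figure, and Section 7.5 states no detectable effect for the phase contrast. Where smokers truly switch, the result is inflation of a real fall.

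Finally, bag handling may be covered in the Manual of Procedures (Section 8.3.1), the collection instruction card (Section 7.2.2) or the visit checklists (Section 11.3.3), none of which is available here. The scoring rule for the primary outcome still belongs in the analytic plan.

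**Conclusion.** The concern holds in conditional form and should be fixed. As written, the plan cannot tell a smoke-free switch-phase day from an unreturned bag. Bias toward switching follows if unreturned bags are counted as zero and return is worse in the switch phase than at baseline. Under those two assumptions, with no true change and 10 to 15 cigarettes per day, a 5% differential loss shifts the H1a contrast by 0.5 to 0.75 per day. In the simplified simulation, with that loss in the switch phase only, a true null was rejected in roughly half to nine-tenths of runs. The actual loss rates are unknown, so the documents establish the ambiguity but not the size or direction of any error in this trial.

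**What to change.** 1. In both phases, require every dated filter bag back, empty or not, and drop the conditional wording for the bags at Days 11, 14, 17 and 21.
2. Log each bag as: filters present (with the count); empty, with the participant confirming no cigarettes that day; or not returned.
3. State in Sections 7.4.3 and 7.5 that a bag not returned is missing, never zero.
4. At the existing visit, record the self-reported cigarette count for those dates. Use it in one sensitivity analysis, and set missing days to the participant's own baseline rate in a second. The second matters because coding as missing removes the bias only if loss is unrelated to the amount smoked.
5. Reconcile the two CO criteria, then flag zero-filter days that precede a raised reading. Section 4.1 verifies status at 50% of the Intake value, while Section 7.4.1 takes a reading above 5 as smoking. Intake CO must be at least 10, so half of it is 5 or more. A participant with an Intake value of 20, for example, could meet the first criterion at 10 and still count as smoking under the second.

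The cost is a short visit-log entry and a few sentences of analysis text, with no new visits, since the bags are already issued. There will be slightly more missing days. Individual filters withheld from a bag that is returned will still go undetected.

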7.5 Analytic Plan

Sample size. Hypotheses will be tested with 80% power using a two-sided type-1 error of 5%. The primary outcome is the longitudinal daily count of cigarettes from baseline to the end of the IQOS switch phase. Using simulation methods, with correlated negative-binomial random numbers ($r=0.6$ within subject) and a longitudinal (GEE) negative binomial model, we calculated that we can detect a slope (change per day) of 0.1 cigarettes, or a change of 1.5 cigarettes per day across the two-week switch period. With a lower correlation ($r=0.3$), that detectable effect becomes a slope of 0.15 (change per day) or 2.0 cigarettes per day across the switch period. The secondary outcome is motivation to quit smoking (contemplation ladder), which will also be modeled longitudinally. The contemplation ladder itself has a historical standard deviation of approximately 3.0, and a correlation of 0.3. Our sample of 100 will allow us to detect a change of 0.7 in the contemplation scale in a baseline to end of study comparison.

Data analysis. Prior to analyses, we will: (a) screen the data for data entry errors, (b) check for outliers, and (c) assess the extent and type of missing data, and select the most appropriate method for dealing with the missing data. We will create all summary scores needed for the analysis, and check that the distributional assumptions are met. We will assess for participation biases and differences between participants retained and lost. Analyses will be conducted using Stata software (StataCorp, College Station, Texas).

The primary outcome is a daily count variable, the number of cigarettes smoked each day. The distribution of cigarettes smoked per day is expected to be over-dispersed (and perhaps zero inflated), because of the study instructions for participants to switch to IQOS heat-sticks for a 14-day period, and the expectation that the majority of participants will have various levels of dual use. The number of IQOS HeatSticks used each day is also a count variable. Participants may have days where they only use IQOS HeatSticks, only smoke cigarettes, and days where they use both. We will accomplish the measurement portion of Aim 1 by summarizing the daily frequencies of cigarettes only, partial switching, and complete switching. Distributional assumptions of all regression methods will be examined in the data set ahead of the analysis to ensure that the best and most representative error model is used. We will examine demographic and other variables for any association with the outcomes or predictors. Those found to be

CONFIDENTIAL

This material is the property of the University of Pennsylvania. Do not disclose or use except as authorized in writing by the study sponsor

associated with outcomes ($p=0.2$) will be included in the model either to correct for confounding or to control error.

The goal of Aim 1 is to evaluate the effects of IQOS use on cigarette smoking behaviors. For the primary analysis, we will analyze the longitudinal counts of cigarettes using mixed models (Gaussian or negative binomial as appropriate). The model will include predictors of time (continuous or discrete), and study phase (baseline versus switch period). We will also include candidate controlling variables (demographic and clinical).

H.1.a. states that IQOS use will decrease the number of cigarettes smoked per day relative to baseline. We do not expect IQOS to replace all cigarettes, and we will measure the use of cigarette smoking only, dual use, and IQOS only use (complete switching). H.1.a. will be tested using the z-score corresponding to the contrast between baseline and switch periods (phase). **H.1.b.** states that the reduction in number of cigarettes smoked per day will be associated with the number of IQOS HeatSticks used. For H.1.b., we will add the daily IQOS use to the model predicting cigarette use, and test using the z-score corresponding to the daily IQOS HeatStick count by phase interaction.

H.1.c. will test whether IQOS use decreases smokers' motivation to quit cigarette smoking. This hypothesis will be examined using mixed models. Predictors will include time (baseline, end of study), and H1c will be tested using the z-score corresponding to the baseline to end of study comparison. Secondarily, we will test cumulative IQOS use as the predictor for change in motivation to quit smoking as measured by the contemplation ladder.

The goal of Aim 2 is to examine which subjective and objective effects of IQOS predict cigarette smoking. **H.2.** will test whether participants who report lower IQOS risk perceptions, greater craving relief, greater withdrawal relief, greater IQOS subjective reward, and have a higher relative reinforcing value of IQOS will smoke fewer cigarettes per day during the 14-day switching period. For H.2., we will remove the daily IQOS counts from the model to avoid confounding, and evaluate the laboratory measures from days 6 and 7 (i.e., IQOS risk perceptions, craving relief, withdrawal relief, subjective reward, and reinforcing value of IQOS relative to cigarettes) for entry in to the model as predictors, using the significance of the corresponding z-score.

8 Risks / Benefits

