4.3 Rationale

4.1.1 Rationale for within-subject design

We chose a within-subjects design for several reasons. First, our proposed aims and hypotheses reflect intra-individual change across time. Baseline smoking rate will be established across five days of ad-libitum smoking. Cigarette smoking subsequent to the introduction of IQOS will be compared to each participant's baseline smoking rate (Day 1-5 vs. Day 8-21, see Figure 1). Randomly assigning smokers to continue to smoke their own cigarettes or to switch to IQOS in a between-subjects design is inconsistent with our aims. Second, we do not expect daily cigarette consumption to change in a group of smokers instructed to continue smoking as usual. Third, utilizing a within-subjects design allows us to maximize statistical power and take advantage of the high within-individual correlation of the primary outcome measure so that we can detect differences in smoking behaviors as participants switch to IQOS.

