4.1.4 Rationale for providing IQOS, but not smokers' own brand of cigarettes

IQOS will be provided to participants at no cost, but cigarettes will not. This decision is based on methodological, budgetary, and logistical reasons. One, it is not feasible to maintain every variety of cigarette brand that smokers use. Two, we are interested in how IQOS use impacts smoking behavior. By providing cigarettes, we may alter cigarette smoking behavior by implying that we expect participants to smoke their usual brand in addition to IQOS. Three, smokers who purchase IQOS in the natural environment are likely to have a limited supply of cigarettes available, because their intent is to switch to IQOS. As such, not providing a 14-day supply of cigarettes maximizes external validity.

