7.2.4 Day 7 Visit

During the Day 7 Visit, (Duration: ~2 hours) participants will:

1. Arrive at the Center at 9:00 AM after having abstained from smoking overnight.
2. Perform a CO breath assessment and concomitant medication review.
3. Have their overnight smoking abstinence (10-hours) verified by a CO measurement of 50% of Intake visit's CO value
4. Be asked questions about use of marijuana, other tobacco products (besides cigarettes), or vaping of any substance including tobacco/nicotine or other drugs in the past month.
5. Complete questionnaires:
 - Adverse Events Form (Open-Ended AEs)
6. Be introduced to and briefly practice the Relative Reinforcing Value of IQOS (RRVI) computerized lab task.
7. Complete computerized lab task: Relative Reinforcing Value of IQOS (RRVI).
8. Complete a standardized one-hour wait period in the laboratory, then complete required IQOS use in the lab.
9. Review instructions for IQOS use with a member of the research staff.
10. Receive an IQOS 3.0 holder and charger, a 7-day supply of regular and/or menthol HeatSticks, and 14 date-stamped zipped baggies for daily collection of spent filters and HeatSticks (7 for spent cigarette filters, 7 for used HeatSticks).
11. Be provided with instructions to switch completely from smoking combustible cigarettes to using IQOS.
12. Review written instructions for the collection and storage of used tobacco HeatSticks with a member of the research staff.

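### H1a is tested by a phase term in a model that also contains time, without a time coding or averaged contrast, so the test need not be the Day 1-5 versus Day 8-21 difference; the stated power is for a slope

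*Combined protocol and SAP*

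**What the plan says.** Section 4.1.1 (Rationale for within-subject design) says that smoking after IQOS is introduced will be compared with each participant's "baseline smoking rate (Day 1-5 vs. Day 8-21, see Figure 1". This is a comparison of two period averages.

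Section 7.5 (Analytic Plan) describes the primary model as a mixed model, Gaussian or negative binomial: "The model will include predictors of time (continuous or discrete), and study phase (baseline versus switch period". H1a "will be tested using the z-score corresponding to the contrast between baseline and switch periods (phase". The section gives no origin or centring for time, no time-by-phase term, and no rule for averaging the contrast over days.

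On power, the same section says "Hypotheses will be tested with 80% power using a two-sided type-1 error of 5" percent, and then that "we can detect a slope (change per day) of 0.1 cigarettes, or a change of 1.5 cigarettes per day across the two-week switch period". That figure is for a within-subject correlation of 0.6; at 0.3 it becomes a slope of 0.15, or 2.0 cigarettes per day. No detectable effect is given for the phase contrast.

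**The concern.** Phase and study day are strongly related by design: every baseline day precedes every switch day. When both are in the model, the meaning of the phase coefficient depends on how time is coded. Under some codings it is the difference between period means. Under others it is a jump left over after a trend has been removed, or it cannot be estimated as a separate term.

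This is the primary hypothesis. Two analysts who both follow Section 7.5 could report different effects from the same counts, with different standard errors. The shape of the fall decides how far apart they are, and the protocol expects some gradual change: Section 4.1.3 reports that in earlier studies most change came within the first 12 days of product use. The power statement does not settle the matter, because it concerns a slope.

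**Working it through.** **The plan's own figure.** Assume the slope is estimated on the 14 switch days with exchangeable correlation. Then detectable slope = 2.80 × SD × √[(1−r)/(N × 227.5)], where 2.80 is 1.96 + 0.84 and 227.5 is the sum of squares of days 8-21 about their mean. Section 7.5 gives no SD, mean or dispersion for the daily count and attaches no N to the slope. (The plan elsewhere has 40 in the summary, 100 in the motivation-ladder sentence and 160 in Section 4.2.) Solving for the SD:

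| N | SD for slope 0.10, r = 0.6 | SD for slope 0.15, r = 0.3 |
|---|---|---|
| 40 | 5.4 | 6.1 |
| 100 | 8.5 | 9.7 |
| 120 | 9.3 | 10.6 |
| 160 | 10.8 | 12.2 |

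So the figure cannot be reproduced, but it is not shown to be wrong. The totals do not identify the days used: 0.1 × 14 = 1.4 against the stated 1.5, and 0.15 × 14 = 2.1 against 2.0.

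**What the phase term estimates.** Use the 19 counted days, with mean day 3.0 at baseline and 14.5 in the switch period. With an intercept, phase and one linear study-day term, least squares gives

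phase coefficient = mean difference − 11.5 × fitted slope.

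The fitted slope is the pooled within-phase slope, with denominator 10 + 227.5 = 237.5.

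- *Pure step of −5.* Slope 0; phase −5.00; true difference −5.00.
- *Half the fall immediate, the rest over an assumed 12-day ramp (per unit of total fall).* The ramp averages (78/12 + 2)/14 = 0.607 over the switch days, so the mean difference is −(0.5 + 0.5 × 0.607) = −0.804. The fitted slope is −0.5 × 17.42/237.5 = −0.0367. Phase = −0.804 + 11.5 × 0.0367 = −0.382, which is 48% of the true difference. If one third of the fall is immediate the share is 24%; if three quarters, 77%.
- *Step of −5 on day 8, then a rebound of +0.3 per day.* Mean difference = −5 + 0.3 × 6.5 = −3.05. Slope = 0.3 × 227.5/237.5 = 0.2874. Phase = −3.05 − 11.5 × 0.2874 = −6.35.
- *Steady drift of −0.1 per day from day 1, no IQOS effect.* Mean difference = −0.1 × 11.5 = −1.15. Phase = 0.

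**Other codings.** With time centred within each phase, the phase coefficient is the mean difference in every case above. With 19 day indicators plus phase, the design has rank 19 for 20 columns, so a separate phase term is aliased. The contrast of averaged days can still be estimated.

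**Precision.** Per unit of within-subject variance, the phase variance factor is 1/5 + 1/14 = 0.2714 without study day. With study day it is 0.2714 + 11.5²/237.5 = 0.8283. The ratio is 3.05. If the effect varies between subjects, with variance k times the within-subject variance, k is added to both factors, and the ratio falls to 2.07, 1.72 and 1.44 for k = 0.25, 0.5 and 1. Some variation is likely, given "the expectation that the majority of participants will have various levels of dual use".

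**Calibrated to the stated slope at r = 0.6, k = 0.** If the slope uses the 14 switch days, within-subject variance/N = (0.1/2.80)² × 227.5 = 0.290. The detectable phase effect is 2.80 × √(0.2714 × 0.290) = 0.79 without study day and 2.80 × √(0.8283 × 0.290) = 1.37 with it. If the slope instead uses all 19 days without a phase term (sum of squares 724.7), these become 1.40 and 2.45.

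On the first calibration, a half-immediate total fall of 6 cigarettes per day has over 99% power under either coding; at k = 1 it is 88% with study day and about 100% for the mean contrast. A half-immediate total fall of 1.5 has 21% with study day against 99% for the mean contrast, or 12% against 51% at k = 1.

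**The case against.** The intended contrast is partly stated. Section 7.5 speaks of a contrast between periods and Section 4.1.1 fixes the days, so a statistician could reasonably read H1a as a period average. With discrete time that is the natural estimable contrast, and centring within phase delivers it. The distortion needs common linear study day, which the plan does not commit to. This stands as a reason to treat the problem as an open definition. It does not remove the problem, because study day is an ordinary reading of continuous time and no averaging is written down.

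Adjusting for trend is also defensible. The study has no control group, and a mean contrast counts any steady drift as effect. Section 4.1.1 expects no change in smokers who continue as usual, which weakens this argument but does not dispose of it.

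The design also favours an early drop. Participants will "Be provided with instructions to switch completely from smoking combustible cigarettes to using IQOS", and "IQOS will be provided to participants at no cost, but cigarettes will not". For a pure step the phase term is unbiased under any of the estimable codings considered here.

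A reader might infer that H1a is underpowered. The documents do not support that: the inputs are missing, and large falls would be detected under either coding. A reader might also infer that the coding will be chosen once the data are seen. Section 7.5 ties inspection of the data to distributional assumptions and covariates, and says nothing of the kind about time.

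**Conclusion.** The point holds in a conditional form. As written, the H1a test does not fix which quantity is estimated. Under common linear study day the phase term departs from the Day 1-5 versus Day 8-21 difference by 11.5 times the fitted slope, in either direction, with variance up to 3.05 times larger. Under a full day factor, a separate phase coefficient is not identified. The 80% power is for a slope whose days, mean, dispersion and N are not stated.

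The 3.05 ratio assumes exchangeable correlation and an effect common to all subjects. The 48% and -6.35 figures rest on assumed profiles.

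A reader might go further and infer that the test would show the wrong sign under the plan's own slope. A flat baseline, no immediate step and a fall of 0.1 per day from day 8 would indeed give +0.35 against a true -0.75. But Section 7.5 does not say that its slope is confined to the switch days or that there is no immediate drop. The immediate share below which the sign turns also depends on the assumed ramp: about 19% for a 12-day ramp that has already begun on day 8, and about 26% if it starts from zero on day 8. Nor is the error always towards understatement, as the rebound case shows.

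This should be fixed. For large falls the harm lies mainly in the reported estimate, less in detection.

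**What to change.** Define H1a as the model-based mean of days 8-21 minus the model-based mean of days 1-5, from one prespecified model. Either of these will do:

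- phase with time centred within phase;
- day as a factor, with weight 1/14 on each switch day and -1/5 on each baseline day.

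With a log link, average the predicted daily counts, not the log coefficients. Report the within-switch slope separately, and the study-day-adjusted phase term as a sensitivity analysis. State the small downside: in this uncontrolled before-after design the mean contrast absorbs any steady drift unrelated to IQOS.

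Restate the detectable effect for this contrast with the N, mean and dispersion used, or label the present figure as power for a slope and say which days it covers.

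The cost is a few lines in Section 7.5 and, if the power is restated, a rerun of the simulation. No new data are needed.
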